9.0 Patient Withdrawal and Trial Discontinuation

9.1 Criteria for Subject Off-Therapy

Subjects may be withdrawn from the study treatment for the following reasons:

- Subject completes all protocol defined therapy- 27 cycles
- Relapsed neoplastic disease
- Subject or guardian withdraws consent to continue study drug
- Subject develops an intercurrent illness that precludes further participation, or requires a prohibited concomitant treatment
- The Investigator withdraws the subject in the subject's best interests
- Subject is lost to follow-up (defined as the inability to contact the subject on 3 separate occasions over a period of 2 weeks)
- Administrative reasons (e.g., the subject is transferred to hospice care)
- An adverse event, which in the opinion of the Investigator, precludes further trial participation or fulfills the protocol requirements for withdrawal (e.g., the development of dose limiting toxicity despite a reduction in protocol therapy for a previous episode of dose limiting toxicity)
- Death

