10.2 Statistical Analysis

This is an open label, single agent, multicenter, study for patients with neuroblastoma that are in remission.

The following data sets will be used in this study:

- All enrolled and eligible subjects (ITT) population: All eligible subjects who have a signed informed consent form.
- All treated and eligible subjects (Safety evaluable) population: All subjects who received at least one dose of study drug
- All eligible subjects treated to first evaluable time point with evaluation completed (generally 3 cycles) (as Treatment Efficacy) population, unless subjects have reached the study endpoint of progression of disease at an earlier time point.

Efficacy analyses will be performed on the Treatment evaluable population. Safety analysis will be performed on the Safety and Efficacy evaluable population.

10.3 All baseline patient characteristics will be summarized in a tabular format. Safety data will be described for all subjects receiving at least one dose of DFMO. Safety data will include values for hematology, serum chemistry, vital signs, and adverse events. The proportion of subjects experiencing adverse events, serious adverse events, dose limiting toxicities and treatment delays will be summarized. Enrollment to study will not pause at interim analysis time points.

Sample Size and Analysis:

Stratum 1:

A 70% 2-year EFS rate was selected as the Phase I baseline rate. The baseline 70% EFS rate at 2-years was based upon published data by Yu et al. (82). It is hypothesized that DFMO will increase the 2-year EFS rate to 80% which represents an approximately 10% increase in the duration of the EFS rate at 2-years. Assuming a directional 5% one population binomial test, a sample size of $n = 127$ patients will be required to achieve an 80% power to detect this 2-year difference in EFS (70% vs 80%).

The comparison of the biomarker prevalence rates assumes that the Stratum 1 cohort will experience a relapse rate of 30% and thus a 70% non-relapse rate at up to two years of follow-up. It is also assumed that the corresponding prevalence of an elevated biomarker will be 60% for the relapse group and 30% in the non-relapse group, respectively. This hypothesized prevalence difference will be detectable with 85% power with an overall sample size of N=127 patients (38 relapse and 89 non-relapse) using a Fisher's Exact Test and a non-directional Type I Error level of 5%.

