The sequential biomarker data over the course of treatment for each patient will be classified as elevated or not based upon the following *a priori* study criteria and blinded to patient progression status. Elevation of the biomarker is defined as diacetylspermine levels > 500nmol/gm creatinine on 2 consecutive urine levels. The biomarker prevalence rates for the patients who progress (estimated to be n= 38) and those who do not progress (estimated n=89) over the two years of the trial treatment will be compared using a Fisher's exact test of the equality of the two EFS prevalence rates implemented with a 5% two-tailed Type I error level. A 95% exact confidence interval for the absolute difference in prevalence rates along with a 95% exact confidence interval for the odds ratio for the resulting prevalence rates will be obtained to complement the formal hypothesis testing. Since OS will also be a secondary outcome for comparing the utility of the biomarker prevalence, time-to-event analyses will also be implemented using the Kaplan-Meier approach initially using the *a priori* biomarker definition. These initial time-to-event analyses will then be supplemented with a Cox proportional hazard modeling effort using the quantitative biomarker assessment to allow for an exploratory analysis of other cut-point definitions that can be used to contrast with that of the original *a priori* definition. Potential confounding clinical measures that are identified for the recurrent and non-recurrent patients will be incorporated in a limited fashion using Cox proportional hazard models that also include the biomarker effect. This exploration of confounders will need to be limited due to the anticipated small sample sizes. Data from this stratum will guide the statistical design for a Phase II study in this patient population.

Stratum 2:

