12.2 Biological Correlative Studies Sample Instructions

Subjects will have the following required urine samples sent.

12.2.1 Required Urine Polyamines Collection:

At screening, on Days 1 and 15 of Cycle 1, and on Day 1 of cycles 2-27, urine polyamines will be collected.

- A. First morning void urines will be collected using a clean catch method in containers and placed at 4°C until transported to the laboratory. Collection of 15ml is ideal, but lab can accept amounts down to a minimum of 1 (one) ml.
- B. Specimens will be transferred to 15ml polypropylene conical tubes (use multiple 15ml tubes as needed) and stored at -80°C until analysis for the dc-SAM and polyamines. Samples should be kept at 4°C (either in refrigerator or on ice pack during shipping) until frozen and must be frozen within 48 hours from collection time. If unable to freeze within 48 hours please note this on the container along with time before frozen.

- C. Samples will be batch shipped on a Monday (send after approximately 20 samples are collected) and sent on dry ice to:

[name]

Pediatric Oncology Translational Research Laboratory

Coopers Landing

[name]

[name]

Ph: [contact]

[contact]

Subjects will have the following optional (recommended) blood and bone marrow samples sent.

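### Elevated status is taken from all on-treatment urines, but relapse ends sampling: the Fisher comparison is biased and the Kaplan-Meier groups contain immortal time

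*Combined protocol and SAP*

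**What the plan says.** Section 10 (Sample Size and Analysis, Stratum 1) gives each patient a single label: "The sequential biomarker data over the course of treatment for each patient will be classified as elevated or not". The rule is "Elevation of the biomarker is defined as diacetylspermine levels > 500nmol/gm creatinine on 2 consecutive urine levels". The assessor is blinded to progression. Label prevalence in patients who progress and "those who do not progress (estimated n=89) over the two years of the trial treatment will be compared" by a two-sided 5% Fisher's exact test. For overall survival, "time-to-event analyses will also be implemented using the Kaplan-Meier approach" with the same label. Cox models on the quantitative marker follow as exploratory work; they are not said to be time-dependent.

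Section 12.2.1 fixes the sampling: "At screening, on Days 1 and 15 of Cycle 1, and on Day 1 of cycles 2-27, urine polyamines will be collected". The off-therapy visit (Section 7.9) lists no urine, and Section 7.10 is survival contact only. Section 9.1 lists "Relapsed neoplastic disease" among the reasons for coming off treatment. Overall survival starts at the first dose (Section 10.5).

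On power: "This hypothesized prevalence difference will be detectable with 85% power with an overall sample size of N=127 patients (38 relapse and 89 non-relapse"), for prevalences of 60% and 30%. The same section says of the treatment effect: "It is hypothesized that DFMO will increase the 2-year EFS rate to 80" per cent.

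**The concern.** The window for the label and the window for the outcome are the same two years, and the outcome closes the label's window. A patient who stays in remission keeps giving urines, each a new chance of a high consecutive pair; a patient who relapses stops. Even a marker unrelated to relapse will then be found elevated more often in non-progressors. Blinding prevents subjective classification but leaves the number of urines unequal.

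In the Kaplan-Meier analysis, a patient labelled at month 12 had to survive to month 12, yet those months count in the elevated group from day 1.

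Correlating urinary polyamines with progression is a secondary objective (Section 3.2.1), and Section 10 says the Stratum 1 data will inform the design of a later study. Truncated sampling can reverse or hide a real association. A rise caused by emerging relapse pushes the other way, so the net error cannot be read from the planned result.

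**Working it through.** **The plan's own power.** Inputs (Section 10): 38 and 89 patients, 60% and 30% elevated, two-sided 5% Fisher test. Summing the probability of every rejecting table gives 86.8%, so the stated 85% reproduces. This assumes the label is equally obtainable in both groups. The test's actual size at 30% in both groups is 3.9%.

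**Urines per patient.** Completer: 1 (screening) + 2 (cycle 1) + 26 (cycles 2 to 27) = 29. Progressor, assuming a constant hazard and 70% two-year EFS:
- Hazard = −ln(0.7)/730.5 = 0.000488 per day.
- Probability of relapse by day 756 (27 × 28) = 1 − exp(−0.000488 × 756) = 0.309.
- Median relapse day among relapsers = −ln(1 − 0.309/2)/0.000488, about day 343.
- Urines by then: 3 + 12 (cycles 2 to 13, since 1 + 28 × 12 = 337) = 15.

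The simulated mean is 15.1 if relapse is found at once, and 17.2 if it is found at the scans after cycles 3, 6, 9, 13, 20 and 27.

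**False rejection with no true association, relapse found at scans.** Simulation of 127 patients, 2500 replicates per setting. The marker is normal with a patient effect (ICC assumed), and the cut-off is set so that 30% or 60% of completers have a high consecutive pair. The plan assumes 30% for non-relapsers; 60% is a sensitivity case.

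| ICC | 30% elevated, EFS 70% | 60% elevated, EFS 70% | 30% elevated, EFS 80% |
|---|---|---|---|
| 0 | 22% | 55% | 17% |
| 0.3 | 14% | 25% | 11% |
| 0.5 | 11% | 17% | 8% |
| 0.7 | 8% | 11% | 5% |
| 0.9 | 4% | 5% | 4% |

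At 70% EFS and ICC 0.7 or below, at least 96% of the rejections make elevation look protective. If 20% of non-progressors also leave early, the rates at 30% / 60% elevated are 17% / 36% at ICC 0 and 8% / 10% at 0.5.

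**Relapse found at once, 30% elevated over a full schedule, EFS 70%.** The middle columns drop the null: 60% of relapsers would be elevated on a full schedule, but sampling stops at relapse. The last columns use the label as written in a log-rank test of time to relapse, with no true association.

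| ICC | Relapsers labelled (null) | Odds ratio | Fisher rejects | Relapsers labelled (60% on full schedule) | Power | Log-rank rejects | Hazard ratio |
|---|---|---|---|---|---|---|---|
| 0 | 15.7% | 0.43 | 35.6% | 34% | 6% | 40% | 0.48 |
| 0.3 | 19.0% | 0.55 | 21.1% | – | – | – | – |
| 0.5 | 21.0% | 0.62 | 14.7% | 47% | 40% | 17% | 0.65 |
| 0.7 | 23.1% | 0.70 | 9.8% | 51% | 56% | 11% | 0.73 |
| 0.9 | 26.0% | 0.82 | 5.6% | 55% | 72% | 7% | 0.84 |

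**Immortal time.** Only patients high on both the screening and the day 1 urine carry none. In the simulations they are 5–7% of elevated patients at ICC 0 and 54–69% at ICC 0.9.

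**Remedy under no association.** Twelve settings (ICC 0, 0.5, 0.9; 30% or 60% elevated; both detection rules), 1200 replicates each: the time-dependent Cox score test rejects in 4.3–6.1%, and Fisher at a day 84 landmark in 1.8–4.6%. A landmark log-rank at day 85 rejects in 4.7–5.2%, with hazard ratios 0.99–1.00.

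**Power at the trial's own hypothesis.** 127 × 0.20 = 25.4 relapses. Exact Fisher power for 60% against 30% is 76.0% at 25/102 and 78.4% at 26/101.

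**The case against.** The size of the bias is unknown. ICC 0 means a patient's monthly urines are unrelated to each other, which nothing in the documents supports; at ICC 0.9 there is almost no inflation. The bias is also milder at 80% EFS, and the plan's own prevalence for non-relapsers is 30%, not 60%. All of this stands, and is why a range is shown.

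The bias runs against the plan's hypothesis of more elevation in relapsers; false rejections in the hypothesised direction were below 1%. That also stands. The practical danger is a diluted or reversed association more than a convenient false positive.

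Section 9.1 says patients may be withdrawn at relapse, no rule for stopping urine is written, and part of the urine text in Section 12.0 is redacted. The end of sampling is therefore inferred from a schedule written by treatment cycle, but the readable text lists no later urine.

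The documents give no overall survival rates, so immortal time is quantified only for time to relapse. The exploratory Cox models could be time-dependent, but the plan does not say so, and the Fisher test and Kaplan-Meier curves are fully specified as they are.

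The choice of analysis is partly a choice of estimand, and time-dependent Cox does not separate a rise that precedes relapse from one caused by undetected relapse, since later scans are seven cycles apart. These are limits of the remedy; they do not rescue the planned comparison.

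**Conclusion.** The concern holds. As written, the rule lets progression shorten the period in which a patient can be labelled, and the survival curves start the clock before most labels can be assigned. Under the plan's 30% prevalence, 70% EFS, constant hazard and scan detection, the nominal 5% Fisher test rejects in between 4% (ICC 0.9) and 22% (ICC 0) of trials with no association. The range is 5.6% to 35.6% if relapse is found at once. With immediate detection, a true 60% against 30% contrast would be detected with 6% to 72% power instead of 86.8%. Where in these ranges the trial falls depends on within-patient variability, which is not given. The primary EFS test is unaffected.

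The stated power is correct for its inputs. Its use of 30% relapse, where the trial hypothesises 20%, is a minor sensitivity point on which this conclusion does not depend.

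**What to change.** - Make the main biomarker analysis a Cox model for EFS, and likewise for OS, with elevation as a time-dependent covariate that switches on at the second consecutive value above 500 nmol/g creatinine.
- Restrict any Fisher or Kaplan-Meier display to a pre-specified landmark, for example the end of cycle 3: patients event-free then, labelled only from urines up to then, with the survival clock restarted there.
- Report the power of the planned Fisher comparison as about 87% at 70% EFS and 76–78% at 80% EFS. Do not carry these figures over; compute the power of the Cox and landmark analyses from a stated hazard ratio and event count.

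The cost is SAP wording and a little programming, on the same samples. A day 84 landmark loses 1 − exp(−0.000488 × 84) = 4% of patients and 0.040/0.309 = 13% of progressors, and uses only the first few urines. The remedy has been checked for false-positive control only; its power is not yet known.

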3.0 Study Objectives

3.1 Primary Objective:

3.1.1 To evaluate the preventative activity of DFMO as a single agent in patients that are in remission based on: Event free survival (EFS)

3.2 Secondary Objectives:

3.2.1 Correlation of urinary polyamine levels with progression of disease in neuroblastoma.

3.2.2 To evaluate the preventative activity of DFMO as a single agent in patients with neuroblastoma who are in remission based on:

- Overall Survival (OS)

3.2.3 To continue to determine the safety and tolerability of DFMO as a single agent and in pediatric and young adult patients with high risk neuroblastoma that is in remission.

3.2.4 To evaluate the pharmacokinetics (PK) of new DFMO formulation in a minimum of 10 patients.

3.2.5 Biological Correlates to minimally include: 1) Urine: polyamine levels and blood inflammatory markers, 2) Blood- microRNA analysis as predictor of DFMO effect; ODC SNP analysis in DNA isolated from nucleated cells; circulating tumor cell analysis, and explorative biomarker analysis 3) Bone Marrow- flow cytometry of minimal residual disease of tumor; explorative biomarker analysis

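### The urinary polyamine objective asks about levels, but its only formal test uses one ever/never label at 500 nmol/gm creatinine, and the planned model of the level is exploratory

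*Combined protocol and SAP*

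**What the plan says.** Section 3.2.1 states the objective as "Correlation of urinary polyamine levels with progression of disease in neuroblastoma". Section 12.2.1 makes the urine sampling mandatory and frequent: "At screening, on Days 1 and 15 of Cycle 1, and on Day 1 of cycles 2-27, urine polyamines will be collected". That is up to 3 + 26 = 29 samples per patient.

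The analysis is in the Stratum 1 text under Sample Size and Analysis (section 10.3). Each patient receives one classification: "The sequential biomarker data over the course of treatment for each patient will be classified as elevated or not". The rule is fixed in advance and applied blind to progression status: "Elevation of the biomarker is defined as diacetylspermine levels > 500nmol/gm creatinine on 2 consecutive urine levels". The sample size assumes that "the corresponding prevalence of an elevated biomarker will be 60% for the relapse group and 30% in the non-relapse group", and the plan calls the difference "detectable with 85% power with an overall sample size of N=127 patients (38 relapse and 89 non-relapse) using a Fisher's Exact Test" at a two-sided 5% level. Exact 95% intervals for the difference in prevalence and for the odds ratio accompany the test.

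Time-to-event work follows, introduced by way of overall survival. Kaplan-Meier analyses use the same label. A supplementary Cox model is then described as "using the quantitative biomarker assessment to allow for an exploratory analysis of other cut-point definitions". Limited adjustment for confounders by Cox models that include the biomarker effect is also foreseen.

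**The concern.** The objective is about a quantity, and the quantity is measured about monthly. The test that carries the error rate and the power statement sees only whether a patient ever had two consecutive values above 500. A patient whose values run just above the cut is treated like one far above it, and likewise below. If the Fisher test is negative, the result speaks to this one cut and not to whether levels track progression. The quantitative model that could answer that question has no prespecified form and no stated estimate, and its stated purpose is to look for other cut-points.

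A second difficulty does not depend on the distribution of levels. The label accumulates over treatment. Section 9.1 lists relapse as a reason to come off therapy, so a patient who relapses early supplies fewer scheduled urines and has fewer chances of two consecutive elevations. Part of the contrast between progressors and non-progressors is then a contrast in length of observation, in the direction that hides an association.

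The plan says data from this stratum will inform the design of a later study, so the way this result is framed matters.

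**Working it through.** **Inputs from section 10.3.** Elevated in 60% of relapsers and 30% of non-relapsers; 38 and 89 patients; Fisher's exact test, two-sided 5%; 2-year EFS of 80% hypothesised under DFMO.

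**Reproducing the plan's figure.** Power is the sum, over all pairs (x, y) with two-sided Fisher p ≤ 0.05, of Bin(x; 38, 0.60) × Bin(y; 89, 0.30). The result is 86.8%, or 84.7% if the one-sided p-value is doubled. The stated 85% stands.

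**The split if DFMO works as hypothesised.** The 38/89 split is 127 × 0.30 = 38.1. With 80% EFS it becomes 127 × 0.20 = 25.4, so about 25 and 102 (treating every event as a progression). The same enumeration gives 76.0%.

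**Illustration of what the label gives up.** The documents give no distribution or SD for diacetylspermine, so this part is assumption. Suppose each patient had one continuous summary value, with the two groups placed so that 60% and 30% exceed the cut. The shift is F⁻¹(0.70) − F⁻¹(0.40):

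- normal: 0.524 + 0.253 = 0.778 SD
- logistic: ln(0.7/0.3) − ln(0.4/0.6) = 0.847 + 0.405 = 1.253, an odds ratio of 3.5
- Laplace: 0.511 + 0.223 = 0.734
- pure step: levels differ only in the proportion above 500

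Power of a two-sided 5% Wilcoxon test, from 20,000 simulated trials per cell:

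| Assumed shape | 38/89 (Fisher 86.8%) | 25/102 (Fisher 76.0%) |
|---|---|---|
| Normal shift | 97.5% (+11) | 91.9% (+16) |
| Logistic shift | 95.6% (+9) | 88.9% (+13) |
| Laplace shift | 88.4% (+2) | 77.1% (+1) |
| Pure step at 500 | 76.8% (−10) | 64.9% (−11) |

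If relapsers' values are also more spread out, the gain shrinks. On the normal scale it is about 6-7 points with an SD 1.5 times larger and about zero with an SD twice as large.

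**Dependence of the label on the number of urines.** Assume independent urines with the same chance p of exceeding 500 in every patient. The chance N(n) of no two consecutive elevations in n urines follows N(n) = (1−p)N(n−1) + p(1−p)N(n−2), with N(0) = N(1) = 1. Setting 1 − N(29) = 0.30 gives p = 0.118. Then:

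- relapse during cycle 6, with 3 + 5 = 8 urines: 1 − N(8) = 9%
- relapse during cycle 13, with 3 + 12 = 15 urines: 1 − N(15) = 16%

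With no biological difference at all, the early relapser is labelled elevated far less often than the patient who completes treatment. Real urines from one patient will be correlated, so these figures show direction and not size.

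**The case against.** The case for the plan is substantial. This is a secondary objective in a single-arm phase II trial. The cut was set in advance, applied blind to progression, and requires two consecutive values, which guards against one noisy spot urine. The power statement reproduces and exact intervals are promised. All of that stands. It is why the Fisher test should stay as the powered analysis.

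Four stronger readings are tempting, and the documents do not support them.

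- A reader might infer a single power loss of roughly 9-16 points. That merges two splits. At 38/89 the gain cannot exceed 100 − 86.8 = 13.2 points. Nor does it hold for location shifts in general, as the Laplace row shows. Part of the gap also comes from Fisher's conservatism: an unconditional exact test (Boschloo) on the same label has 88.4% and 79.0%, so about 1.6 and 3.0 points are not due to dichotomising.
- A reader might infer that the quantitative data are discarded. They are not. The Cox model is planned, and its link to overall survival alone is only one reading of an ambiguous paragraph. What is missing is a prespecified role for the level in relation to progression.
- A reader might say that the cut has no source. The urine-analysis text in section 12.0 is blacked out, so nothing can be concluded from its absence.
- A reader might want the level test placed first, with Fisher tested only if it succeeds. Under a pure step at 500, with the Wilcoxon test as gatekeeper, formal success of Fisher falls from about 87% to 75% at 38/89, and from about 76% to 61-62% at 25/102. The safeguard would fail where it is needed.

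Finally, the 60% and 30% are prevalences of an event over a series, not tail areas of one measurement, and the Wilcoxon figures are not the power of a time-updated Cox model.

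**Conclusion.** The concern holds as a mismatch between objective and formal analysis. Objective 3.2.1 is about levels, no formal test uses the level, and the planned quantitative model is exploratory and aimed at other cut-points. There is no error in the stated power.

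The size of the efficiency cost cannot be fixed from the documents. Under assumed normal or logistic shifts with a rank test it is about 9-11 points at the planned split and 13-16 at the split implied by 80% EFS. Other plausible shapes bring it to nearly nothing or reverse it. The firmer reasons to act are that the stated question has no prespecified estimate, and that an ever/never label is tied to length of follow-up. Both can be addressed with samples the protocol already requires. This is an inexpensive improvement worth making, not a defect that threatens the trial.

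**What to change.** In the Stratum 1 text of section 10.3:

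- Keep the a priori 500 nmol/gm creatinine Fisher comparison and its exact intervals as the powered two-sided 5% test, not conditional on any other result.
- Add a prespecified Cox model for time to progression, with log diacetylspermine (per gm creatinine) as a continuous, time-updated covariate from the scheduled urines. Report the hazard ratio per doubling with a 95% confidence interval as the estimate for objective 3.2.1. Because it compares patients at risk at the same time, it does not reward longer follow-up with more chances of elevation.
- If formal error control is wanted for the level model, test it after Fisher at the same 5% level, so that no alpha is split and Fisher's power is unchanged.
- Leave the search for other cut-points exploratory.

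The cost is SAP wording, one more model and a routine check of the log-linear form. No new samples, visits or patients are needed. One limitation remains: if risk truly jumps only at 500, the level model will be the weaker of the two analyses, so both should be reported.

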6. Subjects who, in the opinion of the investigator, may not be able to comply with the safety monitoring requirements of the study, or in whom compliance is likely to be suboptimal, should be excluded.

Additional criteria:

Subjects willing to participate in the correlative biologic studies will sign an additional consent form to provide bone marrow and blood for analysis.

- Stratum 1: Subjects that are in remission at the end of upfront therapy defined as chemotherapy (5-7 cycles), surgery as indicated, consolidation therapy as indicated, radiation therapy as indicated, anti-GD2 antibody therapy with retinoic acid up to 6 cycles.
- Stratum 2: Subjects that are in remission after any previous relapse or refractory therapy

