Based upon tabled median EFS times all patients presented by Santana et al. (Cancer, June 15, 2008) for first and second recurrence times, a median first recurrence time of 8.7 months is equivalent to a 14.8% EFS at two years, and the median time to a subsequent second recurrence of 3.8 months is equivalent to an EFS rate of 1.3% at two years assuming an exponential time-to-event model. Assuming that two thirds of the relapse patient population will have had only a single relapse and that the other third of the patients will have had two or more relapses, then a weighted average of these two EFS rates (14.8% and 1.3%) equals 10.3%. A 10% historical EFS rate for two years was assumed for simplicity. Examination of an increase in EFS will require a sample size of n = 33 subjects in Stratum 2 to test whether treatment with DFMO can prolong the overall estimated EFS at two years to 30% from the 10% two years estimate for the above historical data in this patient population. The sample size is based upon a one sample binomial test of proportions with a power 80% and a 5% two -tailed Type I error level.

An observation of 7 or more patients with at least a two year EFS rate out of the $n = 33$ patients will result in the rejection of the null hypothesis of a 10% EFS in favor of the alternative of a 30% two year EFS rate. An exact binomial 95% confidence interval for the two year estimated EFS will complement the prior formal two-stage hypothesis test. Since the actual EFS time-to-event data is derived from the times to recurrence, a Kaplan-Meier analysis of the time-to-event data analysis will be conducted, and the median time to recurrence and a 95% confidence for this value will be obtained to supplement this EFS point estimate. Since this group of Stratum 2 patients will consist of patients with prior single and multiple recurrence histories, EFS and time to event data will be examined by prior recurrence histories. In particular, the impact of prior recurrence history on the time to recurrence will be explored using Kaplan-Meier analysis and Cox proportional hazard models. The response to DFMO therapy and subsequent recurrences will also be explored in combination with prior recurrence histories using Cox models.

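### The Stratum 2 null of 10% rests on an unsourced 2:1 relapse mix, but the cut-off of 7 of 33 stays fixed whatever mix enrols

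*Combined protocol and SAP*

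**What the plan says.** Section 10 (Sample Size and Analysis, Stratum 2) converts two published median times into two-year rates with an exponential model. For the first, "a median first recurrence time of 8.7 months is equivalent to a 14.8% EFS at two years". The second, a median of 3.8 months to a further recurrence, becomes 1.3%. The plan combines them under an assumed mix, "Assuming that two thirds of the relapse patient population will have had only a single relapse". The remaining third is taken to have relapsed at least twice. No source is given for these weights. The text reports that "a weighted average of these two EFS rates (14.8% and 1.3%) equals 10.3" per cent, and rounds to 10%. With an alternative of 30% and 33 evaluable patients, the null is rejected if at least 7 are event-free at two years. The synopsis gives the same rule.

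Section 5.0 defines Stratum 2 as "Subjects that are in remission after any previous relapse or refractory therapy". It sets no quota or cap by number of relapses. Section 10 recognises that the stratum is mixed and says that "EFS and time to event data will be examined by prior recurrence histories", using Kaplan-Meier and Cox models. None of that work alters the null rate, the cut-off or the formal test.

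**The concern.** The expected number of successes under an inactive drug depends on how many patients have had one relapse and how many have had more. The plan settles that proportion in advance and never replaces it with the observed one. If more than two thirds of patients have had a single relapse, the rule calls an inactive drug active more often than designed. If fewer have, it misses a real effect more often. EFS is the primary endpoint, this is Stratum 2's only formal decision rule, and the stratum has no concurrent control to absorb the error.

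There is also a gap in the reference rates. The entry definition admits patients in remission after refractory disease. Those who never relapsed belong to neither component, so the weighted average gives them no null rate.

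**Working it through.** **Inputs, all from Section 10, Stratum 2:** medians 8.7 and 3.8 months; weights 2/3 and 1/3; null 10%; alternative 30%; n = 33; reject at 7 or more.

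**Step 1: the plan's null.** Under an exponential model, EFS at 24 months = 0.5^(24/median).
- 0.5^(24/8.7) = 14.8%
- 0.5^(24/3.8) = 1.3%
- (2/3 × 14.8) + (1/3 × 1.3) = 10.3%

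The printed figures reproduce. The ratio of the two rates is 14.8/1.3 = 11.4.

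**Step 2: the plan's rule at its own null.** For X ~ Bin(33, 0.10), P(X ≥ 7) = 4.2%. For X ~ Bin(33, 0.30), P(X ≥ 7) = 90.6%. The printed rule therefore meets a 5% upper tail if the null is right.

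**Step 3: the same rule as the mix varies.** With n1 single-relapse and n2 multiple-relapse patients (n1 + n2 = 33), the null count is S = Bin(n1, 0.148) + Bin(n2, 0.013), with mean 0.148·n1 + 0.013·n2. Tail probabilities come from the exact convolution. The assumed mix is 2/3 × 33 = 22 single and 11 multiple.

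**Step 4: cut-off re-derived from the mix.** This is the smallest c with P(S ≥ c) ≤ 5%, the upper-tail level that the printed rule meets.

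**Step 5: power at the re-derived cut-off, two ways.**
- (a) The alternative is held at 30%, using Bin(33, 0.30).
- (b) The hazard ratio implied by 10% to 30%, ln 0.30 / ln 0.10 = 0.52, is assumed to apply in both subgroups. The alternatives become 0.148^0.52 = 36.8% and 0.013^0.52 = 10.3% (unrounded exponent 0.5229).

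| Single/multiple | Mean null | P(S ≥ 7) | Cut-off at 5% | Its tail | Power (a) | Power (b) |
|---|---|---|---|---|---|---|
| 16/17 | 7.8% | 1.0% | 6 | 3.6% | 95.9% | 82.4% |
| 17/16 | 8.3% | 1.3% | 6 | 4.5% | 95.9% | 85.1% |
| 22/11 (plan) | 10.3% | 4.4% | 7 | 4.4% | 90.6% | 86.7% |
| 23/10 | 10.7% | 5.3% | 8 | 1.8% | 81.8% | 78.5% |
| 26/7 | 11.9% | 8.8% | 8 | 3.4% | 81.8% | 86.1% |
| 30/3 | 13.6% | 15.0% | 9 | 2.7% | 69.6% | 85.6% |
| 33/0 (bound) | 14.8% | 20.8% | 9 | 4.6% | 69.6% | 90.9% |

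There is almost no slack: one single-relapse patient above 22 takes the upper tail past 5%. In the other direction, keeping the cut-off at 7 with a 16/17 mix gives power of 68% under assumption (b), against 82% with the re-derived cut-off of 6.

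**The case against.** The plan makes no arithmetic error. It states the 2:1 mix openly as an assumption, and the rule holds 5% in the upper tail if that mix enrols. Every single-arm test against a fixed historical rate carries uncertainty of this kind. The planned analyses by recurrence history and the exact confidence interval would let a careful reader notice a favourable mix. Close to the assumed mix the inflation is modest: 5.3% at 23/10 and 6.3% at 24/9. All of this stands and limits the size of the point. It does not remove it, because the mix, unlike the historical rates, will be observed in the trial and the formal test ignores it.

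A reader might infer three stronger things that the documents do not support.

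- **That the false-positive rate is 20.8%.** This requires all 33 patients to have had one relapse. Section 10 itself expects both single and multiple histories, so 20.8% is a bound and not a forecast.
- **That enrolment will favour single relapse.** Section 1.0 speaks of relapsed patients reaching a second remission, which is suggestive, but no section gives an expected enrolled mix. The error can move either way.
- **That the cut-off should be 8 to 10.** Cut-offs of 8, 9, 10 and 10 for 22/11, 26/7, 30/3 and 33/0 come from also tightening the upper tail to 2.5%. Whether a cut-off of 7 agrees with the stated two-sided 5% level is a separate question and should not be folded into this one.

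**Conclusion.** The point holds as a weakness in the decision rule. On the plan's own component rates, a fixed cut-off of 7 has an error of 1.0–1.3% at about half single relapse, 4.4% at the assumed mix, and 8.8% to 15.0% at mixes of 26/7 to 30/3. The planned exploratory analyses do not protect the test. The omission of never-relapsed refractory patients from the null follows from the entry definition alone and does not depend on any mix.

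The calculation takes 14.8% and 1.3% as true. Both are historical values, converted from medians by an exponential assumption, and reweighting does not repair them. If the remission requirement itself changes prognosis, the component rates shift as well.

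**What to change.** Amend the Stratum 2 text in Section 10, and the synopsis to match, before outcomes are reviewed:

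1. Define the null expectation as 0.148·n1 + 0.013·n2 over the patients in the efficacy analysis. Take the cut-off from the exact distribution of the sum of the two binomials at a stated upper-tail level. At 5% this gives 6 for 17/16, 7 for 22/11, 8 for 26/7, and 9 for 30/3 and 33/0. The same formula serves if the evaluable number is not 33.
2. Classify each patient from baseline history, and lock the classification before outcomes are reviewed, so that the cut-off cannot be driven by results.
3. State how never-relapsed refractory patients are counted: reported separately, or given a null rate with its justification.
4. Give the source of the 2:1 planning mix, or label it as a planning assumption only.

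The cost is wording. Section 7.2 already collects medical history and prior cancer treatments at screening, and the planned subgroup analyses need recurrence history anyway.

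The plan should also state the downside. With the alternative held at 30%, power falls from 90.6% (cut-off 7) to 81.8% (8) or 69.6% (9) when the mix is more favourable than assumed. If the hazard ratio of 0.52 applies in both subgroups, which is an assumption, power is about 86% at 26/7 and 30/3 and 91% at 33/0. It dips to 78.5% at 23/10, where the cut-off has just stepped up.
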